5.2. Handling of Study Interventions

Due to the nature of the intervention, participants cannot be masked.

There is no "training fidelity" plan given the nature of this intervention.

There is no "intervention fidelity" plan given the nature of this intervention.

5.3. Concomitant Interventions

We do not have any concomitant interventions.

5.4. Adherence Assessment

There is no "adherence assessment" plan given the nature of this intervention.

6. STUDY PROCEDURES

6.1. Schedule of Evaluations

Measure	Baseline	1-3 month follow-up	3-6 month follow-up
Aim 2			
Feasibility (Participants meeting eligibility criteria are identified and mailed intervention materials)	X		
Acceptability (Participants find the intervention acceptable)		X	
Implementation Success (Taper plans for CNS-active medications are documented in the participants' medical records)		X	X
Aim 3			
Feasibility of obtaining outcomes data from the medical records (e.g., falls, nursing home placement, etc.)			X

6.2. Description of Evaluations

The pilot study evaluation (Aim 2) will assess 1) feasibility of reaching the target population, 2) acceptability of the intervention, and 3) success of intervention implementation.

Intervention feasibility will be measured by the ability to pull baseline data such as participant contact information, eligibility/ineligibility criteria, and demographics. If no more than 30% of intervention materials are “returned to sender,” we will deem it feasible to reach the target population.

Intervention acceptability will be measured by responses on returned questionnaires. If at least 65% of returned questionnaires indicate the intervention is acceptable and [if applicable] open-ended comments are positive >50% of the time, we will deem the intervention to be acceptable to the target population.

Intervention implementation success will be measured by documentation of a plan to taper in the “sig” field in the participant’s medical record; if at least 35% of participants have a documented taper plan, we will consider the intervention to have been successfully implemented.

Feasibility of obtaining outcomes data from the medical record will be assessed in Aim 3. Outcomes (clinical and utilization) data will be summarized and presented as percent of the study sample with the event (e.g., percent with a medically treated fall; percent with any ED visit or hospitalization, percent with a skilled nursing facility stay). Time to first medically treated fall will also be recorded.

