5. STUDY INTERVENTIONS

5.1. Interventions, Administration and Duration

Aim 2

The study design is a one-arm, pragmatic pilot trial. The intervention will be implemented with up to four clinics and up to 120 OPWD and their care partners. The intervention consists of an educational brochure about a CNS-active medication that the OPWD has been prescribed along with decision support for that individual's PCP. To assess the acceptability of the intervention, a brief questionnaire will be mailed to the OPWD shortly after mailing of the intervention materials. Follow-up for outcomes ascertainment will start at the time of mailing of intervention materials to eligible participants.

1. After the sample has been identified, the study team will send a packet to all eligible participants containing:
 - a. A cover letter addressed to the participant and any care partner they may have. The letter will also contain a study phone number with voicemail to call if either participant or care partner has questions. This voicemail line will be monitored by study staff;
 - b. Educational brochure for the medication class that the participant has been prescribed on a chronic (3 months or longer) basis;
 - c. For most drug classes, a corresponding non-pharmacological self-care sheet, previously approved for STOP FALLS that has been modified based on dementia care partner input (Aim 1 interviews).
2. At the same time, the study team will use the Epic (electronic medical record) "staff message" functionality to send a message letting the PCP know that their patient is included in the study and a link to the EBPO of the relevant medication class. The purpose of this message is to enable the PCP to be prepared to have conversations with participants about their medication use and for these conversations to be guided by the evidence and talking points in the EBPO. The timing of these messages is not aligned with an upcoming clinic visit; it is anticipated that a participant/care partner may initiate the conversation with the provider on their own time schedule.
3. When the participant/care partner receives the mailed packet, they can choose to read the materials or not. Reading all the materials in the packet should take approximately 10 minutes. If they choose, they can discuss the information in the brochure with their PCP.

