4. Approximately 1-3 weeks after brochure mailing, the study team will send a brief questionnaire to OPWD and their care partners to ascertain intervention acceptability including the perceived usefulness of the educational materials and the likelihood of starting conversations about their medications with their providers. Care partner sociodemographics will also be obtained via this questionnaire for descriptive purposes. If the participant/care partner choose to complete and return the questionnaire, that activity should take approximately 5 minutes. (see **Supplements/Appendices: Participant questionnaire**)
5. Returned questionnaires will be data-entered, and a survey response dataset will be created.

Aim 3

The automated data pulls and chart review associated with Aim 3 involve data collection for the pilot trial to establish the feasibility of using pragmatic methods to ascertain the following outcomes: 1) medically treated falls (primary outcome), 2) all-cause emergency department visits and hospitalizations (secondary outcome), and 3) nursing home placement (secondary outcome).

Automated data pull

1. The study programmer will modify existing code from STOP-FALLS to pull data from KPWA automated data sources for the following three outcomes:
 - 1) medically treated falls (primary clinical outcome), 2) all-cause emergency department visits and hospitalizations (secondary outcome), and 3) nursing home placement (secondary outcome).
2. An analytic dataset will be created and outcomes data summarized. We anticipate this will take 3-6 months.

Medication taper ascertainment from medical records

1. The study programmer will modify existing code from STOP-FALLS to create flags indicating which participants’ medical records have deprescribing text in the “sig field” (i.e., prescribing instructions) for each CNS-active medication.
2. The KPWA study team members ([name] and [name]) will review up to a 20% random sample of records to adjudicate whether or not the flags correctly identified evidence of a medication taper, completing the following shell table for each record:

Field	Description	Notes:

Study ID	Pre-populated study ID	
ConsumerNo	Pre-populated Consumer Number	PHI
Medication class	Pre-populated med class (e.g. opioid, TCA, benzo)	
Date	Pre-populated date	PHI
Taper flag	Pre-populated (yes/no)	Did the program identify a potential deprescribing plan for the sig field?

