9.5. Data Analyses

We will summarize measures of feasibility and acceptability using binary outcomes and calculating proportions and 95% confidence intervals using simple descriptive analysis. For our primary endpoint of implementation success, following the framework proposed for pragmatic pilot trials,³⁹ if 35% have a documented taper plan, the trial will be “green” lighted to move forward to a confirmatory study; if 20%–<35% have a documented taper plan, it will be “yellow” lighted, meaning that the intervention needs to be modified if to move forward; and if <20% have a documented taper plan, it will be “red” lighted, meaning that the intervention is a “no go”. The same framework will be applied across secondary endpoints. We will examine differences by relevant sociodemographic characteristics (e.g., race, ethnicity, sex) for each outcome using the same criteria.

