16. SUPPLEMENTS/APPENDICES

Participant questionnaire

The first question lets us know who is filling out this questionnaire. Is the person filling out this questionnaire:

- Someone who assists a Kaiser Permanente enrollee who may have memory difficulties with their medical care
- A Kaiser Permanente enrollee who may have memory difficulties
- Other; _____

The next question is about the medication information packet that you received in the mail recently. Please choose the response that best describes your impression of the medication information packet.

The medication information packet...

	Completely disagree	Disagree	Neither agree nor disagree	Agree	Completely agree
Meets my approval					
Is appealing to me					
Is likeable					
Is welcome to me					

Please tell us about yourself

1. Which of the following describes your race? Please select all that apply

- American Indian/Alaskan Native
- Asian
- Black or African American
- Native Hawaiian/Other Pacific Islander
- White
- You describe yourself as; _____

2. Do you consider yourself to be:

- Hispanic or Latino
- Not Hispanic or Latino

3. What is your age?

- Less than 65
- 65-74
- 75-84
- 85-94
- 95 and older

4. Sex

- Female
- Male
- You describe yourself as; _____

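### The 65% acceptability verdict pools forms from people with dementia and from care partners, so it can reflect mainly one group, although question 1 of the form already separates them

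*Combined protocol and SAP*

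**What the plan says.** Section 6.2 gives a two-part rule and a single verdict. The first part is "If at least 65% of returned questionnaires indicate the intervention is acceptable". The second, which applies only if there are comments to judge, is that "open-ended comments are positive >50% of the time, we will deem the intervention to be acceptable to the target population". Neither part distinguishes who filled in the form. Section 1.1 names both OPWD and care partners in the primary objective, while section 11.2 uses the term target population for OPWD.

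Section 5.1 describes the recipients in two ways. The introduction to Aim 2 says "a brief questionnaire will be mailed to the OPWD shortly after mailing of the intervention materials". Step 4 says "the study team will send a brief questionnaire to OPWD and their care partners to ascertain intervention acceptability".

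The questionnaire in section 16 states: "The first question lets us know who is filling out this questionnaire". One option is "Someone who assists a Kaiser Permanente enrollee who may have memory difficulties with their medical care", another is "a Kaiser Permanente enrollee who may have memory difficulties", and the third is an open Other. Section 10.1 makes the form anonymous and not linkable to other study data.

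Section 9.5 plans a proportion with a 95% confidence interval for acceptability, and adds: "We will examine differences by relevant sociodemographic characteristics (e.g., race, ethnicity, sex) for each outcome". Respondent type is not mentioned there.

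**The concern.** OPWD and care partners are different raters. The rating items are in the first person, so a care partner's form records the care partner's own view and is not a proxy for the enrollee's. A single percentage over all returned forms is a weighted average of the two groups' opinions, and the weights come from who chooses to send a form back, which the study does not control.

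If the two groups agree, pooling does no harm. If they differ, the verdict depends on the mix as well as on opinion. The pilot could then report the packet as acceptable to people with dementia when most of those who answered did not find it so, or the same for care partners if OPWD return most of the forms. That conclusion would be carried into the planned full-scale trial. Because the forms cannot be linked to other data, question 1 is the only route to respondent type, and the plan collects it without using it in the rule or the analysis.

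**Working it through.** **Is there a plan figure to reproduce?** Not for this rule: the 65% threshold has no calculation behind it. The only derived figure, n = 78 in section 9.2, concerns taper plans (20% against 35%, 90% power, one-sided 5%). The normal approximation gives [(1.645·√(0.20·0.80) + 1.282·√(0.35·0.65))/0.15]² = 71.6. The continuity correction, (71.6/4)·(1 + √(1 + 2/(71.6·0.15)))², gives 78.1. So 78 is reproduced, and nothing below depends on it.

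**Inputs.** From the documents: the 65% threshold over all returned forms (6.2), two kinds of recipient (5.1, step 4), and three respondent categories (section 16). The documents give no return rate, respondent mix or group-specific rates, so these are assumptions, shown over a range. Each form is treated as favourable or not favourable.

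**Formula.** Let w be the care-partner share of returned forms, c the care-partner rate and d the OPWD rate. The pooled rate is w·c + (1 − w)·d.

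**Illustration (assumed returns).**

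| Mix | Care partners at 80% | OPWD at 35% | Pooled |
|---|---|---|---|
| 40 care partners, 20 OPWD | 32 | 7 | 39/60 = 65% |
| 20 care partners, 40 OPWD | 16 | 14 | 30/60 = 50% |

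Opinions are the same in both rows. Only the mix changes, and the 65% part of the rule goes from met to not met. In the first row OPWD alone are 7/20 = 35%, exact 95% CI 15% to 59%, wholly below 65%.

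**How low can OPWD be?** Setting the pool to 65% gives d = (0.65 − w·c)/(1 − w).

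| Care-partner share w | d if c = 80% | d if c = 90% |
|---|---|---|
| 50% | 50% | 40% |
| 70% | 30% | 6.7% |

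At an 80% share and c = 80%, d is (0.65 − 0.64)/0.20 = 5%.

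**Allowing for chance.** A binomial simulation (200,000 runs) used assumed true rates of 80% for care partners and 40% for OPWD, with 30 to 120 forms returned. The probability that the pool reaches 65% is:
- 0.13 to 0.30 at a 50% care-partner share
- 0.66 to 0.81 at 70%
- 0.82 to 0.97 at 80%

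With 60 forms and a 70% share it is 0.76, and in 0.74 of all runs the pool passes while the observed OPWD rate is below 65%. The arithmetic is symmetric if OPWD return most of the forms.

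**What a split would show.** Take 60 forms, with care partners 36/42 and OPWD 6/18. The pool is 42/60 = 70% (exact 95% CI 56.8% to 81.2%). By question 1, care partners are 85.7% (71.5% to 94.6%) and OPWD 33.3% (13.3% to 59.0%).

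**Price of a threshold in each group.** On the same 42/18 split, if true acceptability is 75% in both groups, the chance of passing falls from 0.97 (pooled) to 0.79 (both at or above 65%). At 80% it falls from 0.998 to 0.94.

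**The case against.** The packet goes to a household under one cover letter addressed to the participant and any care partner, and the introduction to Aim 2 in 5.1 has the questionnaire mailed to the OPWD. One form per household, completed by whoever handles the post, is a plausible reading, and a pooled household rating would then be defensible. This stands as far as it goes. But step 4 names both groups as recipients, the plan nowhere makes the household the unit, and 6.2 words the verdict for the target population. The ambiguity is a reason to say whose rating is meant.

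The list in 9.5 is introduced as examples, so a split by respondent is not excluded. True, but it is not planned, and a secondary comparison would leave the 6.2 verdict unchanged. Nor does the comments condition protect either group: it is equally unsplit, and the form as reproduced in section 16 shows no comment field.

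The illustration is constructed, and at an even mix the pooled rule often fails anyway. That stands: the effect needs groups that disagree and, for a frequent misleading pass, a lopsided mix.

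Split rates come from self-selected respondents, cannot be linked to dementia severity or household, and may rest on few forms. That also stands, and it limits how firmly any group result can be worded.

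A reader might infer that each group must be made to reach 65% before the pilot can proceed. The documents do not support that. They set no such requirement, the primary endpoint is the documented taper plan (9.2, 9.5), and a dual threshold makes the criterion materially harder to meet even when both groups find the packet acceptable.

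**Conclusion.** The concern holds as a matter of what the rule permits. Section 6.2 gives one verdict on forms from two kinds of rater, and the variable that separates them is collected but unused in the rule and the analysis. Under the assumed 40/20 mix, the 65% part of the rule is met with OPWD at 35%, and reversing the mix moves the pool from 65% to 50%. With assumed true rates of 80% and 40%, the chance that the pool passes runs from 0.13 to 0.97, depending on the mix and the number of forms.

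Three stronger readings are not supported:
- That OPWD will find the packet unacceptable, or that care partners will dominate returns. The documents give no data on either.
- That 39/60 satisfies the whole rule. It satisfies the 65% part; the comments condition, where applicable, is separate.
- That anonymity distorts the mix, or that the pilot exists to adapt the materials. Voluntary return sets the mix, and anonymity only prevents recovering respondent type from elsewhere. Adaptation belongs to Aim 1; the pilot assesses feasibility, acceptability and implementation.

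This is a worthwhile, inexpensive improvement to the conclusion on acceptability. It does not bear on the sample size or the primary endpoint.

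**What to change.** In 6.2 and 9.5:

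1. Report the acceptability proportion with its 95% confidence interval by question 1 (enrollee, care partner, other), with the number of forms in each, alongside the pooled figure.
2. State before data are seen whose rating the 65% verdict describes.
3. Do not claim acceptability to OPWD, or to care partners, from the pooled figure when that group's own result falls below 65%.
4. Do not make a pass in both groups the go/no-go rule.

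In 5.1, reconcile the introduction to Aim 2 with step 4 on who is sent the form, and say whether a household receives one form or two. Two anonymous forms from one household would be correlated and could not be matched.

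The cost is wording only: no new data are needed, because question 1 is already on the form. The downsides are small groups with wide intervals, respondents who are self-selected within each group, and conclusions that may differ between OPWD and care partners.

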9.2. Sample Size and Randomization

For Aims 2 and 3, our sample size calculations are based on the framework of “green”, “yellow” and “red” lighting for pilot feasibility trials.³⁹ Based on our primary endpoint, which is implementation success,¹⁷ assuming the upper boundary of the “red” zone is 20% and the lower boundary of the “green” zone is 35%, the sample size required for analysis given 90% power and one-sided 5% alpha is $n=78$ (intervention arm only). Specifically, if the true rate is in the “green” zone with a sample size of 78, we have 90% power for the study to not be defined as “red” lighted. We will increase the sample size to 120 to be able to have 90% power across all secondary endpoints as well.

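### Acceptability is concluded for the whole target population from whatever questionnaires come back, and the 90% power statement cannot be verified for it

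*Combined protocol and SAP*

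**What the plan says.** Acceptability is part of the primary objective (section 1.1) and one of three Aim 2 results. Section 6.2 gives the decision rule: "If at least 65% of returned questionnaires indicate the intervention is acceptable". A second condition, used only where it applies, requires more than half of any free-text remarks to be favourable. When the rule is met, the conclusion is drawn for the target population as a whole. The denominator is forms returned. No minimum number or response rate is attached.

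Section 5.1 makes return optional ("If the participant/care partner choose to complete and return the questionnaire"). Section 10.1 makes the questionnaire anonymous, with no study ID, so it cannot be linked to other study data.

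Section 9.5 plans to summarise feasibility and acceptability by "calculating proportions and 95% confidence intervals using simple descriptive analysis". It sets green, yellow and red zones for taper plans, with boundaries at 20% and 35%, and then says: "The same framework will be applied across secondary endpoints". No red boundary for acceptability appears anywhere.

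Section 9.2 derives n = 78 for implementation success and adds: "We will increase the sample size to 120 to be able to have 90% power across all secondary endpoints as well". It does not list those endpoints. Section 9.4.2 names the secondary outcomes as emergency department visits and hospitalizations, and nursing home placement.

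**The concern.** The conclusion is about the target population, but the data are a self-selected subset of unknown size. Two things can go wrong when the rule is followed exactly. With few forms, the 65% point estimate says little about the true proportion. With selective return, the estimate is biased, and a larger number of forms does not correct that. Because forms cannot be linked, responders and non-responders cannot be compared and non-response cannot be modelled at participant level.

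The sample size statement adds a separate difficulty. Power for acceptability depends on the number of forms returned and on the red boundary, and section 9.2 gives neither. This pilot is meant to inform a full-scale trial (sections 9.1 and 14), so an acceptability conclusion that looks firmer than it is would be carried forward.

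**Working it through.** **Inputs from the documents.** Primary endpoint: red 20%, green 35%, one-sided 5%, 90% power, n = 78 (9.2). Acceptability: green 65% of returned forms (6.2). Number mailed: 120 (4.3).

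**Assumptions, because the documents are silent.** Acceptability red boundary 40% to 55%; response 20% to 100% of 120.

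**Step 1: reproduce the plan's figure.** One-sample proportion with p0 = 0.20 and p1 = 0.35:

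n = [1.645·√(0.20·0.80) + 1.282·√(0.35·0.65)]² / 0.15² = 71.6.

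Continuity correction: n/4 · [1 + √(1 + 2/(n·0.15))]² = 78.1. This matches the stated 78.

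**Step 2: same formula for acceptability, p1 = 0.65.** For red 50%, the primary endpoint's 15-point gap:

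[1.645·√(0.50·0.50) + 1.282·√(0.65·0.35)]² / 0.15² = 91.4; continuity-corrected, 97.9.

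| Assumed red | Corrected n | Returns for 90% power | Share of 120 |
|---|---|---|---|
| 40% | 36.0 | 36–37 | about 31% |
| 45% | 56.0 | 56 | 47% |
| 50% | 97.9 | 98 | 82% |
| 55% | 214.2 | about 214 | not reachable |

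Exact binomial power agrees: 91% at 36 returns with red 40%, 91% at 56 with red 45%, and 90% at 98 with red 50%.

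**Step 3: exact power by returns, red 50%.** 24 returns: 36%. 36: 49%. 60: 75%. 78: 84%. 120: 95%.

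**Step 4: precision when the rule is only just met (exact 95% limits).** 16/24: 45% to 84%. 24/36: 49% to 81%. 39/60: 52% to 77%. 78/120: 56% to 73%.

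**Step 5: passing by chance.** If true acceptability is 50% and return is unrelated to opinion, at least 65% of forms are favourable with probability 7.6% at 24 forms, 3.3% at 36 and 1.4% at 60.

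**Step 6: passing by selective return.** Illustration: true acceptability 50%, return 50% among the favourable and 25% among the rest.

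Expected favourable share = 0.5·0.50 / (0.5·0.50 + 0.5·0.25) = 0.250/0.375 = 66.7%.

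At 50% true acceptability, the expected share reaches 65% once the favourable return 0.65/0.35 = 1.86 times as often as the rest. This holds at any sample size.

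**Step 7: what non-return leaves open.** If 39 of 60 forms are favourable and all 120 mailings were delivered, the proportion over the 120 lies between 39/120 = 32.5% and (39 + 60)/120 = 82.5%.

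**The case against.** A reader might infer three stronger claims, and the documents support none of them.

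*That the plan has no measure of precision.* Section 9.5 plans 95% intervals. The gap is only that they play no part in the decision. There is also a second condition, on open-ended comments. It applies only where applicable, and the questionnaire as reproduced in section 16 has free-text blanks only for other and self-description entries, so it may never come into play.

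*That the 90% power is not delivered.* This depends on a red boundary and a response rate that the documents do not state. With red at 45%, 56 returns suffice; with red at 50% and all 120 returned, power is 95%. It is also unclear that the statement covers acceptability, since section 9.2 does not define secondary endpoints and section 9.4.2 uses a similar term for utilization outcomes.

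*That non-return was ignored.* Section 9.2 does not explain how 120 was reached. Since 78/0.65 = 120, an unstated allowance for non-return cannot be excluded. Even so, 78 returns against a 50% red boundary give 84% exact power.

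It is also fair to say that passing by chance is uncommon over 24 to 60 forms, that the 50% and 25% return rates are illustrative, and that nothing in the documents shows return to depend on opinion. Implementation success, not acceptability, is the primary endpoint for progression. All of this limits the size of the point. It does not make a result among respondents a result for the target population.

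**Conclusion.** The point holds in this form: section 6.2 draws a population conclusion from a point estimate among voluntary, anonymous returns, with neither a minimum return nor an interval in the rule. A bare pass at 24 forms is compatible with true acceptability as low as 45%, and a 1.86-fold difference in return is enough to lift 50% true acceptability to the threshold in expectation.

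On power, the supportable conclusion is that the 90% statement cannot be verified for acceptability, if acceptability is covered at all. The required number of returns runs from about 36 to beyond 120 as the assumed red boundary moves from 40% to 55%. At the primary endpoint's 15-point gap it is 98, or 82% of those mailed.

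The point concerns acceptability only. Return-to-sender feasibility is based on mailed packets, and taper plans and clinical outcomes are based on records, so their denominators do not depend on questionnaire return.

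**What to change.** **Sections 6.2 and 9.5.** Word the acceptability conclusion as applying among respondents. Beside the 65% decision, report the number of forms returned, the response rate, the 95% interval already planned, and best-case and worst-case proportions over questionnaires mailed and not returned to sender. Count one form per mailed household. As forms carry no identifier, this has to be arranged at mailing, for example by enclosing a single form.

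**Section 9.2.** Say whether acceptability is among the secondary endpoints. If it is, state its red boundary and give power by number of forms returned in place of the single 90% figure. Otherwise delete the claim for acceptability.

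**Optional.** A lower-confidence-limit criterion could be added to the rule. If so, state its level and disclose that it raises the bar. A two-sided 95% exact limit above 50% needs 18/24 (75%) or 25/36 (69%), and with 24 forms an intervention with 75% true acceptability would fail 39% of the time.

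**Cost.** Wording, a few extra reported figures, and a less favourable statement of power and acceptability. No extra participants.
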